### 6.1 Monitoring Risks

To address subject anxiety or embarrassment due to revealing person information, we have trained research staff who are experienced in working with individuals with schizophrenia spectrum disorders. They have been trained to put subjects at ease, let them take their time, and to conduct interviews in private rooms.

To address the issue of accidental disclosure of personal information to others outside of the research staff, we will identify research subjects by study number on all research documents to minimize the risk of breach of confidentiality. Study documents that must contain personal information, including the informed consent document, and the document that links study ID number to personal identifying information are kept in locked filing cabinets in locked rooms. Research data will be kept on password-

protected drives, and our computer systems are HIPAA compliant. All study staff participate in annual human subject training that includes education about responsibilities to minimize risk that confidentiality may be breached.

Online safety. Privacy and online safety will be managed in accordance with the 'Online social networking' guidelines published by 'Cybersmart', a national cybersafety and cybersecurity education program managed by the Australian Communications and Media Authority (ACMA). Cybersmart is designed to meet the needs of its target audiences young people, parents, teachers and library staff. Information about Cybersmart can be found at <http://www.cybersmart.gov.au/>, while the guidelines are available at <http://www.acma.gov.au/>.

Safe and informed orientation to the system will be a priority for the research team. Peer support specialists, clinicians, and/or a graduate student in the Department of Psychology and Neuroscience at UNC-CH will meet with each participant to provide them with login information, help set up their account and orient them to the Horyzons system, including details of the terms of use. All users of Horyzons will be asked to nominate an emergency contact person, such as a close family member. The terms of use explain to users that information passed onto moderators or communicated within the system that may indicate concerns regarding their wellbeing may be communicated with their treating team or private practitioner. Hard copies of 'Horyzons Terms of Use' will be provided to users which will be made available online and in printed form. Participants will be required to sign the hard copy as well as accepting the terms of use on entry into the system. The system also includes a "report function" which enables users at any time to indicate to the moderator a concern about any material posted by a user, including concern about potential abuse or concerns about the well being of another participant. The moderator will assess the basis of the report and respond accordingly, which can include the removal of the material or deactivation of an account.

In addition, users will be able to "switch off" their profile and hide all of their existing comments on the system should they become concerned about their privacy during their course of participation. The limits of the moderator to respond (e.g., in a timely manner to emergencies) will also be fully explained. In order to protect the privacy of users who discontinue using the system, any accounts that have not been activated for one month may be deactivated following a follow-up telephone call from the moderator. Specifically, our disengagement protocol is such that a participant will receive an email/call/text message if they have not logged onto the platform for two weeks. If another two weeks pass, we will call this person to check in about any potential issues or concerns. If participants do not comply with the guidelines for safe use of Horyzons (e.g., discriminatory comments towards other users) they will be excluded from the system.

Clinical safety. Clinical risk will be managed through manual and automated procedures. Information related to clinical risk will be screened twice daily by moderators (in the morning and late afternoon/evening). This information can include: 1) post made by participants, which disclose evidence of psychotic, depressive or suicidal symptoms; 2) participants reports or complaints of posts made by other users; 3) risk or self-harm related words automatically detected and blocked by the system; and 4)

presence of Early Warning Signs of relapse detected by the regular monitoring of psychotic symptoms implemented within Horyzons.

Any detected increased risk will activate the Horyzons crisis protocol which includes a number of potential actions. Initially, the moderator will conduct a risk assessment based upon available information, inform the research team, and emergency contact nominated by the participant, and liaise with suitable emergency services where necessary. In addition, the system incorporates visible emergency guidelines and contact information (i.e., on every webpage).

An automated keyword system has also been built in Horyzons which will be activated each time a participant posts a contribution containing the words or phrases: suicide, die, kill myself/you/him/her/them, hang myself/you/him/her/them, harm myself/you/him/her/them, snort, shoot up, burn myself/you/him/her/them, cut myself, drown myself/you/him/her/them, stab myself/you/him/her/them, slit, slice, electrocute, shoot myself/you/him/her/them, top myself, jump in front of, jump off, end it all, sleep and never wake up, death, die, asphyxiate, or gas. When these words are detected the contribution will be blocked and the participant will be sent an automated message explaining that the content has been blocked and if they are facing distress then they should contact the emergency contact number as soon possible or if they are not facing distress they may like to consider rephrasing their post. An automated message will also be sent to the Horyzons moderator containing the attempted post.

In addition, a message will be available on each page providing a cell phone number carried by a member of the research team for any emergencies that are related specifically to the use of the Horyzons system (e.g., highly inappropriate use of the system). Further, each page includes an "In case of emergency" link that provides information about ways to contact emergency services (911), the UNC crisis line [contact]), and crisis services (<http://crisisolutionsnc.org/>).

## **6.2 NON-SIGNIFICANT RISK DOCUMENTATION**

The present study has been deemed of non-significant risk (NSR) to participants.

## **6.3 POTENTIAL BENEFITS OF THE RESEARCH TO SUBJECTS AND OTHERS**

While the field is still in its infancy, there is preliminary evidence that online interventions that combine therapy, social networking opportunities and expert and peer moderation may be better received by individuals with first episode psychosis than less integrated approaches. The proposed study will expand this growing body of work by testing the clinical utility of this intervention when implemented as part of mental health care at first episode clinics in North Carolina.

Benefits to clients. The proposed study may increase clients' sense of belonging and social support. Also, if they engage in the therapeutic pathways, they might develop cognitive behavioral and mindfulness-based skills.

**Benefits to providers.** Clinicians and peer support specialists may gain insight into clients' experiences using the platform, including possible barriers to engagement and challenges to disseminating the Horyzons platform within the clinic. This information may prove useful to clinicians as they consider ways to incorporate online interventions and other adjunct services into their existing treatment approaches in the future.

## 6.4 CONFIDENTIALITY OF DATA

Names and associated contact information for potential subjects during the recruitment phase will be stored in a manner similar to that used to store study data. This information will be kept in a locked file cabinet in a locked office in the Department of Psychology and Neuroscience at UNC or within the administrative or secure storage areas of the FEP clinics involved in this project. Contact information will be destroyed immediately after it is ascertained that an individual does not want to participate in the study. Declining participants' names will be retained on a secure password protected network to ensure that the same participant is not contacted more than once regarding participation.

A member of the research team will meet individually with the client in order to explain the components of the Horyzons platform, elicit and answer any questions the client may have, and obtain informed consent. We will also collect information about current suicidal ideation and stability (e.g., recent hospitalizations) to assess eligibility for participation. Persons will also be creating a Horyzons profile and answering questions about character strengths (e.g., curiosity, love of learning), which are embedded in the Horyzons platform. These data will be linked to other sources of information, including the record of their interactions within the Horyzons system (e.g., number of posts/comments on the cafe).

The Horyzons system and data generated by users of Horyzons will be hosted on a secure web server. A range of measures are in place to ensure the security of the Horyzons website and the data generated by users. In addition, the team who developed the web application has placed measures within the application to secure the application and database against unauthorized access. These measures conform to industry best practice as defined by the Open Web Application Security Project ([www.OWASP.org](http://www.OWASP.org)). Feedback interviews/focus groups will be conducted via secure Zoom, and will be digitally recorded (via Zoom or using audio recorders) for the purposes of transcription. These recordings and transcripts will be immediately uploaded to a secure, password-protected server and deleted from local devices. The project electronic database (including all transcripts from interviews/focus groups) will be password protected and stored securely, and will only be directly accessible by the research study coordinators, clinicians and peer support specialists, involved in this project, or PI ([name]).

As this research program is being implemented in clinical settings, it is possible that FEP clinicians will create notes that indicate the participant is involved in the project, describe any issues may arise, etc. that will be connected to their medical record. These documents will be stored in approved medical record systems on HIPAA-compliant computers. If researchers complete inductions or introductions to the site via video conference, the video or audio from these interviews will not be saved or recorded. Audio from qualitative interviews and focus groups will be stored on a secure, password-protected server.

Identifiable data will only be shared with the clinicians of subjects in the study with the permission of the subjects (obtained during informed consent). Clinicians will be contacted if issues arise related to safety during the trial. As part of the informed consent process, all subjects will provide the name and contact info of a clinician that we may contact if we become concerned about their safety (e.g., physical and/or mental health) during the course of the trial. We will not be sharing any confidential information with anybody outside of these clinicians.

Identifiable data will be maintained for 5 years following study completion. At that point, hard copies of identifiable data including consent forms and contact information will be shredded. Electronic data will be de-identified upon entry, with the exception of the subjects' birth dates for the purposes of calculating their exact age.

## 7 SAFETY MANAGEMENT

### 7.1 ADVERSE EVENTS

Client activity on the platform will be monitored daily by the online moderators and PSS. Signs of potential clinical deterioration will be reported to the client's treatment team. It is highly unlikely that clinical deterioration will be attributable to the Horyzons system. However, in the event that this becomes evident (e.g., a participant has clearly communicated that they have incorporated aspects of the Horyzons system into their delusional beliefs) the moderator will communicate this information to the clinical treatment team and/or the principal investigator. The principal investigator will inform the IRB of any concerns regarding adverse events associated with involvement in Horyzons.

### 7.2 SERIOUS ADVERSE EVENTS

Adverse events (AE) will be assessed to determine if they meet criteria for a serious adverse events (SAE). SAE, as defined by the FDA, will be systematically evaluated at each clinic visit. The trial period is defined from the time that the informed consent document is signed until 30 days after the last study visit. All SAE occurring during the trial period (including death due to any cause) or within 30 days after the last study visit will be communicated within 1 day of the investigator becoming aware of the event to designated personnel, using the telephone or fax numbers provided in the Study Reference Manual. Any fatal or life-threatening AE will be reported immediately, but no longer than 1 day from the time the investigator becomes aware of the event. A causality assessment will be provided for all SAEs. Critical follow-up information on SAEs will be provided as soon as it is available, but no longer than 1 day from the time the investigator became aware of the information. Other essential, but not critical, information may be reported within the following 5 days. An SAE, as defined by the FDA for use in clinical trials (<https://www.fda.gov/safety/medwatch/howtoreport/ucm053087.htm>), is an adverse event that satisfies any of the following criteria:

- Results in death.
- Is immediately life-threatening, including potentially life threatening suicidal behavior or suicidal behavior that results in hospitalization.
- Requires inpatient hospitalization or prolongation of existing hospitalization.
- Results in persistent or significant disability or incapacity.
- Is a congenital abnormality or birth defect.

- Is an important medical event that may jeopardize the subject or may require medical intervention to prevent one of the outcomes listed above. Examples would include allergic bronchospasm that requires treatment in an emergency department, or a seizure that does not result in hospitalization.

The causality of SAEs (i.e., their degree of relatedness to study treatment) will be assessed by the investigators.

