For all administration of assessments/interviews, the study coordinator will use screen sharing via secure videoconferencing to complete measures with the participant. Baseline assessment will be completed alongside the review and completion of informed consent and onboarding of participants onto the Horyzons platform. Participants will complete a mid-treatment assessment with the study coordinator or other trained research assistant, which corresponds to approximately 6-8 weeks after onboarding in the first cohort and approximately 12 weeks after onboarding in the second cohort. Participants will also meet with the study coordinator or other trained research assistant for a post-treatment assessment after clients have engaged with the platform for 12 weeks in the first cohort and 26 weeks in the second cohort. At post-treatment, both clients and clinicians (procedures described below) will be provided with an optional feedback form as a way of better understanding their experience with the platform and collecting suggestions for improving the site. Individual feedback interviews with clients will also be completed at post-treatment, lasting 60 minutes. These interviews will address participants' social relationships, experiences with loneliness, and thoughts about connecting with others through Horyzons.

In order to evaluate the extent to which engagement in Horyzons may have impacted participants' perceptions of their social environment, participants will be asked to complete brief psychological measures. In the first cohort at baseline, mid-treatment (6-8 weeks), and post-treatment (12 weeks), participants will complete measures of loneliness (UCLA Loneliness Scale), social support (MOS Social Support Survey), social anxiety (Social Interaction Anxiety Scale), recovery (short form PWS - Psychological Wellbeing Scale), and therapeutic alliance (WAI-I and Perceived Autonomy Support Scale).

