### **4.2 INTERVENTION PERIOD PROCEDURES**

#### **4.2.1 MID-TREATMENT PROCEDURES**

The study coordinator will meet virtually with client participants for approximately 30 minutes to complete the mid-treatment measures. Client participants will complete virtual copies of the UCLA Loneliness Scale, MOS Social Support Survey, SIAS, short form PWS, WAI-I, and Perceived Autonomy Support Scale. Participants in the second cohort only will complete additional measures at mid-treatment (e.g., Questionnaire about the Process of Recovery, Modified Colorado Symptom Index, Social Anxiety Scale for Social Media Users, Twente Engagement Questionnaire). Client participants will be paid \$7.50 via Visa gift card for this 30 minutes of their time.

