#### **4.2.3 ADDITIONAL ASSESSMENT PROCEDURES**

For participants in the second cohort only, the study coordinator will meet virtually with client participants for approximately .5 hours to complete the measures at 1.5 months following baseline (i.e., between baseline and mid-treatment visits) and 4.5 months following baseline (i.e., between mid-treatment and post-treatment visits). Participants in the second cohort only will complete virtual copies of the WAI-I, Perceived Autonomy Support Scale, and Twente Engagement Questionnaire. Client participants will be paid \$7.50 via Visa gift card for this 30 minutes of their time.

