## **9 CONSENT PROCESS**

Research staff will obtain informed consent directly from each subject. Staff obtaining the consent will provide the subject with a written document explaining the testing procedures and risks, and will answer any questions. We have several procedures in place to ensure that prospective participants fully understand the procedures, risks, and protections of the study. First, the consent form is written in easy to understand language. Second, the researcher reads the form to and with the potential subject, and invites questions after each section of the form. Third, the researcher asks the subject a series of questions about the study, such as what they are to do if they no longer want to participate, or what they would do if they experience any stress

during the protocol (this is to be used as comprehension check before consenting). As Horyzons is a fully virtual research study, participants will provide verbal consent as recorded by the study coordinator.

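### Section 7.2 ties SAE evaluation to clinic visits, but every scheduled client assessment is virtual and none lists an SAE enquiry

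*Combined protocol and SAP*

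**What the plan says.** Section 7.2 gives the ascertainment rule: "SAE, as defined by the FDA, will be systematically evaluated at each clinic visit". It then sets the reporting window: "All SAE occurring during the trial period (including death due to any cause) or within 30 days after the last study visit" must be reported, with a one-day clock that starts when the investigator learns of the event. It cites the Study Reference Manual only for telephone and fax numbers. For deaths, Section 7.3 adds a second 30-day anchor, counted from the last day of the intervention.

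The rest of the protocol describes a remote study. Section 9: "As Horyzons is a fully virtual research study, participants will provide verbal consent as recorded by the study coordinator". Section 2.1: "For all administration of assessments/interviews, the study coordinator will use screen sharing via secure videoconferencing to complete measures with the participant". Section 4.2.1 is typical of the procedure sections: "The study coordinator will meet virtually with client participants for approximately 30 minutes to complete the mid-treatment measures". For the extra cohort 2 contacts, Section 4.2.3 lists three scales: "Participants in the second cohort only will complete virtual copies of the WAI-I, Perceived Autonomy Support Scale, and Twente Engagement Questionnaire". The same section places the first of these contacts "between baseline and mid-treatment visits", so the protocol does use the word visit for virtual meetings.

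Hospitalisation is asked about, but for a different purpose. Section 6.4: "We will also collect information about current suicidal ideation and stability (e.g., recent hospitalizations) to assess eligibility for participation".

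**The concern.** The rule depends on an event, the clinic visit, that the study schedule does not contain. If it means routine care appointments, nobody is told to evaluate SAEs there or pass them on. If it means the virtual assessments, the sections that itemise those assessments do not include the question.

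Inpatient hospitalisation is one of the SAE criteria in Section 7.2, and a psychiatric admission in the previous three months bars entry under Section 2.2.1. A client can be admitted without leaving any trace on the platform. Without a standard question, a low SAE count could not be told apart from incomplete capture. That matters to participants' safety and to the stated objective of evaluating the safety and privacy protocol (Synopsis and Section 3).

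**Working it through.** No figure in the plan is in dispute, so the main check sets the sections side by side.

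**1. Scheduled client contacts (Sections 4.1.2 to 4.2.3).**

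| Contact | Cohort | Mode | Contents listed | SAE enquiry listed |
|---|---|---|---|---|
| Baseline | 1 and 2 | Virtual | Consent, HIPAA authorization, demographics and history, scales, orientation | None |
| 1.5 months | 2 | Virtual | Three scales | None |
| Mid-treatment | 1 and 2 | Virtual | Scales | None |
| 4.5 months | 2 | Virtual | Three scales | None |
| Post-treatment | 1 and 2 | Virtual | Scales, feedback survey, interview | None |

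Contacts that list an SAE enquiry: 0 of 3 in cohort 1 and 0 of 5 in cohort 2. Leaving out baseline, 2 and 4 contacts per client could carry one. The Modified Colorado Symptom Index in cohort 2 is a symptom scale, not an SAE question. In-person contact is possible at screening (Section 4.1.1) and consent (Section 6), but neither is follow-up.

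**2. Other routes by which an SAE could become known.**
- Through the platform: daily moderation (2.1, 7.1), a moderation checklist (2.1), and twice-daily risk screening, keyword alerts and symptom monitoring (6.1).
- Triggered by absence: a message after two weeks without login and a telephone call after two more (2.1, 6.1).
- Through the clinics: every client is in care at a participating clinic (2.2.1), clinicians and peer specialists moderate (2.1), and clients name a clinician contact (6.4) and an emergency contact (6.1).

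All give partial detection. None is a stated SAE enquiry. The safety and clinical communication described in Sections 2.1, 6.4 and 7.1 runs from the study to the clinic; no routine return of SAEs is described.

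**3. Recall period if the question joins existing contacts.** Timings are from Sections 2.1 and 4.2.3, with one month taken as 365/12 = 30.4 days.
- Cohort 1: baseline to mid-treatment is 6-8 weeks; mid- to post-treatment is 12 - 8 = 4 to 12 - 6 = 6 weeks. The longest is 8 weeks.
- Cohort 2: contacts fall at about days 46, 84, 137 and 182. The gaps are 46, 38, 53 and 45 days. The longest is 53/7 = 7.6 weeks.

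**4. The 30 days after the last study visit, as a share of the SAE window.**
- Cohort 1: 30/(84 + 30) = 30/114 = 26.3% at 12 weeks; 30/(91 + 30) = 30/121 = 24.8% at 3 months.
- Cohort 2: 30/(182 + 30) = 30/212 = 14.2% at 26 weeks; 30/(183 + 30) = 30/213 = 14.1% at 6 months.

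No client contact is described in this period. These are shares of calendar time, not of events.

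**5. Why the last study visit needs a definition.** Suppose a cohort 1 client misses post-treatment and the term means the last visit attended. Mid-treatment falls at day 42-56, so the window closes at day 42 + 30 = 72 to 56 + 30 = 86. For a client seen at day 84, it closes at day 114. The two readings differ by 114 - 86 = 28 to 114 - 72 = 42 days.

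**The case against.** The strongest reply is that Section 7.2 is itself the commitment. It promises systematic evaluation, Section 4.2.3 shows that visit can mean a virtual meeting, and Sections 4.1.2 to 4.2.3 mainly list measures to complete, so their silence does not cancel 7.2. The study forms and the Study Reference Manual might supply the item. This stands in part: the intention is clear, and absence of the question from the forms cannot be shown. It does not settle the matter, because the protocol does not say which contacts count, who asks, or what is asked.

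Stronger readings are tempting, but the documents do not support them.
- A reader might infer that the 30-day period contradicts the schedule. It does not: 7.2 imposes a reporting duty triggered by awareness and promises no active follow-up. An additional check at the end of the window would be a new contact for each client; it is optional, not a needed correction.
- A reader might infer that platform safeguards never reach that period. They can. A cohort 1 post-treatment visit at day 84 with access to about day 91 leaves 91 - 84 = 7 days of overlap, and under step 5 the whole 30 days can fall within the access period.
- A reader might size the gap by counting the days after an inactive account is deactivated. That does not measure detection. An inactive client posts nothing before deactivation either, deactivation is optional and follows a telephone call, the inactivity contacts reach exactly this client, and the assessments continue.
- A reader might take the safety objective to mean that an SAE rate is an outcome. Sections 5.1 to 5.3 list none, and the objective may refer mainly to the online-safety and crisis procedures in Section 6.1.

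**Conclusion.** The concern holds in a limited form. As written, the SAE rule has no identified point at which it operates: the scheduled client contacts are virtual, none of the 3 (cohort 1) or 5 (cohort 2) lists an SAE enquiry, and no clinic staff are assigned one. An off-platform hospitalisation could therefore go unasked. The documents give no SAE or inactivity rate, so the number missed cannot be estimated. The conclusion rests on the protocol text alone and would be met in large part by an existing form that asks the question. The loneliness and social support analyses are unaffected. The 30-day period and the undefined last visit are secondary wording matters. The change should be made because it is cheap and improves safety capture, not because the plan lacks safety monitoring.

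**What to change.** **Main change.** In Section 7.2, replace the reference to clinic visits with the named virtual assessments: mid- and post-treatment in both cohorts, plus 1.5 and 4.5 months in cohort 2. Add one short fixed question at those contacts and at the existing four-week inactivity call, covering hospitalisation, emergency visit, self-harm or other serious event since the last contact. The hospitalisation enquiry used for eligibility can be reused. If a form already asks this, cite it in 7.2.

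**Secondary wording.** State that SAEs in the 30 days after the last study visit are captured by spontaneous report. Define the last study visit for clients who miss post-treatment. Reconcile the 30-day anchors in Sections 7.2 and 7.3.

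**Cost.** The main cost is staff time, at an assumed 2-5 minutes per contact:
- Synopsis numbers (25 and 37 clients): 25 x 2 + 37 x 4 = 198 contacts; 198 x 2/60 = 6.6 hours to 198 x 5/60 = 16.5 hours.
- Section 2.2 maxima (30 and 60 clients): 30 x 2 + 60 x 4 = 300 contacts; 300 x 2/60 = 10 hours to 300 x 5/60 = 25 hours.

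Time at inactivity calls is extra and cannot be sized, because no inactivity rate is given. The main change needs protocol wording and one form item; it adds no assessment. The remaining limitation is recall over up to about 8 weeks.
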